3.11 Infusion Reactions

The following AE terms, regardless of grade, are considered ECIs and should be reported to the Sponsor within 24 hours of the event:

Allergic reaction

Anaphylaxis

Cytokine release syndrome

Serum sickness

Infusion reactions

Infusion-like reactions

Please note, the AE should be reported regardless of etiology.

Course of Action

Refer to infusion reaction table in the protocol and below.

Infusion Reactions

NCI CTCAE Grade	Treatment	Premedication at subsequent dosing
Grade 1 Mild reaction; infusion interruption not indicated; intervention not indicated	Increase monitoring of vital signs as medically indicated until the subject is deemed medically stable in the opinion of the investigator.	None
Grade 2 Requires infusion interruption but responds promptly to symptomatic treatment (e.g., antihistamines, NSAIDS, narcotics, IV fluids); prophylactic medications indicated for <=24 hrs	
Stop Infusion. Additional appropriate medical therapy may include but is not limited to: IV fluids Antihistamines NSAIDS Acetaminophen Narcotics
 
Increase monitoring of vital signs as medically indicated until the subject is deemed medically stable in the opinion of the investigator. If symptoms resolve within one hour of stopping drug infusion, the infusion may be restarted at 50% of the original infusion rate (e.g. from 100 mL/hr to 50 mL/hr). Otherwise dosing will be held until symptoms resolve and the subject should be premedicated for the next scheduled dose. Subjects who develop Grade 2 toxicity despite adequate premedication should be permanently discontinued from further trial treatment administration.
	
Subject may be premedicated 1.5h (\pm 30 minutes) prior to infusion of pembrolizumab with:
 
Diphenhydramine 50 mg p.o. (or equivalent dose of antihistamine).
 
Acetaminophen 500-1000 mg p.o. (or equivalent dose of antipyretic).

NCI CTCAE Grade	Treatment	Premedication at subsequent dosing
Grades 3 or 4 Grade 3: Prolonged (i.e., not rapidly responsive to symptomatic medication and/or brief interruption of infusion); recurrence of symptoms following initial improvement; hospitalization indicated for other clinical sequelae (e.g., renal impairment, pulmonary infiltrates) Grade 4: Life-threatening; pressor or ventilatory support indicated	Stop Infusion. Additional appropriate medical therapy may include but is not limited to: IV fluids Antihistamines NSAIDS Acetaminophen Narcotics Oxygen Pressors Corticosteroids Epinephrine Increase monitoring of vital signs as medically indicated until the subject is deemed medically stable in the opinion of the investigator. Hospitalization may be indicated. Subject is permanently discontinued from further trial treatment administration.	No subsequent dosing
Appropriate resuscitation equipment should be available in the room and a physician readily available during the period of drug administration. For Further information, please refer to the Common Terminology Criteria for Adverse Events v4.03 (CTCAE) at http://ctep.cancer.gov		

3.12 Follow-up to Resolution

Subjects should be followed to resolution. The Adverse Experience eCRF should be updated with information regarding duration and clinical course of the event. Information obtained from the consulting specialist, including diagnosis, should be recorded in the appropriate AE fields. Free-text fields should be used to record narrative information:

Clinical course of the event

Course of treatment

Evidence supporting recovery

Follow-up to the clinical course

Any treatments administered for the event should also be entered in the Concomitant Medication eCRF.

Enterocolitis	Enterocolitis hemorrhagic	Gastrointestinal perforation
Necrotizing colitis	Diarrhea	
Endocrine (reported as ECI if \geq Grade 3 or \geq Grade 2 and resulting in dose modification or use of systemic steroids to treat the AE)		
Adrenal Insufficiency	Hyperthyroidism	Hypophysitis
Hypopituitarism	Hypothyroidism	Thyroid disorder
Thyroiditis	Hyperglycemia, if \geq Grade 3 and associated with ketosis or metabolic acidosis (DKA)	
Endocrine (reported as ECI)		
Type 1 diabetes mellitus (if new onset)		
Hematologic (reported as ECI if \geq Grade 3 or any grade resulting in dose modification or use of systemic steroids to treat the AE)		
Autoimmune hemolytic anemia	Aplastic anemia	Thrombotic Thrombocytopenic Purpura (TTP)
Idiopathic (or immune) Thrombocytopenia Purpura (ITP)	Disseminated Intravascular Coagulation (DIC)	Haemolytic Uraemic Syndrome (HUS)
Any Grade 4 anemia regardless of underlying mechanism		
Hepatic (reported as ECI if \geq Grade 2, or any grade resulting in dose modification or use of systemic steroids to treat the AE)		
Hepatitis	Autoimmune hepatitis	Transaminase elevations (ALT and/or AST)
Infusion Reactions (reported as ECI for any grade)		
Allergic reaction	Anaphylaxis	Cytokine release syndrome
Serum sickness	Infusion reactions	Infusion-like reactions

Neurologic (reported as ECI for any grade)		
Autoimmune neuropathy	Guillain-Barre syndrome	Demyelinating polyneuropathy
Myasthenic syndrome		
Ocular (report as ECI if \geq Grade 2 or any grade resulting in dose modification or use of systemic steroids to treat the AE)		
Uveitis	Iritis	
Renal (reported as ECI if \geq Grade 2)		
Nephritis	Nephritis autoimmune	Renal Failure
Renal failure acute	Creatinine elevations (report as ECI if \geq Grade 3 or any grade resulting in dose modification or use of systemic steroids to treat the AE)	
Skin (reported as ECI for any grade)		
Dermatitis exfoliative	Erythema multiforme	Stevens-Johnson syndrome
Toxic epidermal necrolysis		
Skin (reported as ECI if \geq Grade 3)		
Pruritus	Rash	Rash generalized
Rash maculo-papular		
Any rash considered clinically significant in the physician's judgment		
Other (reported as ECI for any grade)		
Myocarditis	Pancreatitis	Pericarditis
Any other Grade 3 event which is considered immune-related by the physician		

6. APPENDIX 2 – Past Medical History Related to Dermatologic Event

Past Medical History:

Any preexisting conditions not previously reported (e.g., drug allergy) should be entered into the Medical History eCRF.

1. Does the subject have any allergies? Yes No

If yes, please obtain the following information:

a. Any allergy to drugs (including topical or ophthalmic drugs)? Yes No

List the drug name(s) and describe the type of allergic response (e.g. rash, anaphylaxis, etc):

b. Any allergy to external agents, such as laundry detergents, soaps, poison ivy, nickel, etc.? Yes No

Describe the agent and type of allergic response: _____

c. Any allergy to food? Yes No

Describe the food and type of allergic response: _____

d. Any allergy to animals, insects? Yes No

Describe the allergen and type of allergic response: _____

e. Any other allergy? Yes No

Describe the allergen and type of allergic response: _____

2. Does the subject have any other history of skin reactions, skin eruptions, or rashes? Yes
 No

If so what kind? _____

3. Has the subject ever been treated for a skin condition? Yes No

If so what kind? _____

4. Is the current finding similar to a past experience? Yes No

7. APPENDIX 3 – Presentation of the Dermatologic Event

Presentation of the event:

Collect information on clinical presentation and potential contributing factors. Key information should be summarized and entered on the Adverse Experience eCRF. Any treatments administered should be entered on the Concomitant Medication eCRF.

1. What is the onset time of the skin reaction, skin eruption, or rash relative to dose of study drug? _____

2. Has the subject contacted any known allergens? Yes No

If so what kind? _____

3. Has the subject contacted new, special, or unusual substances (e.g., new laundry detergents, soap, personal care product, poison ivy, etc.)? Yes No

If so what kind? _____

4. Has the subject taken any other medication (over the counter, prescription, vitamins, and supplement)? Yes No

If so what kind? _____

5. Has the subject consumed unaccustomed, special or unusual foods? Yes No

If so what kind? _____

6. Does the subject have or had in the last few days any illness? Yes No

If so what kind? _____

7. Has the subject come into contact with any family or house members who are ill? Yes No

If so who and what? _____

8. Has the subject recently been near children who have a skin reaction, skin eruption, or rash (e.g. Molluscum Contagiosum)? Yes No

9. Has the subject had recent sun exposure? Yes No

10. For the current rash, have there been any systemic clinical signs? Yes No

If so what kind? _____

i. Anaphylaxis? Yes No

ii. Signs of hypotension? Yes No

iii. Signs of dyspnea? Yes No

iv. Fever, night sweats, chills? Yes No

11. For the current rash, has the subject needed subcutaneous epinephrine or other systemic catecholamine therapy? Yes No

If so what kind? _____

12. For the current rash, has the subject used any other medication, such as inhaled bronchodilators, antihistaminic medication, topical corticosteroid, and/or systemic corticosteroid? Yes No

List medication(s) and dose(s): _____

13. Is the rash pruritic (itchy)? Yes No

8. APPENDIX 4 – Focused Skin Examination

Focused Skin Examination:

Key information should be summarized and entered on the Adverse Experience eCRF.

Primary Skin Lesions Description

Color: _____

General description:

Describe the distribution of skin reaction, skin eruption, or rash on the body:

Is skin reaction, skin eruption, or rash resolving or continuing to spread?

Any associated signs on physical examination?

Appendix J: MSD Code of Conduct for Clinical Trials

Merck Sharp & Dohme LLC, Rahway, NJ, USA (MSD)

Code of Conduct for Interventional Clinical Trials

I. Introduction

A. Purpose

MSD, through its subsidiaries, conducts clinical trials worldwide to evaluate the safety and effectiveness of our products. As such, we are committed to designing, implementing, conducting, analyzing and reporting these trials in compliance with the highest ethical and scientific standards. Protection of participants in clinical trials is the overriding concern in the design and conduct of clinical trials. In all cases, MSD clinical trials will be conducted in compliance with local and/or national regulations (including all applicable data protection laws and regulations), and International Council for Harmonisation Good Clinical Practice (ICH-GCP), and also in accordance with the ethical principles that have their origin in the Declaration of Helsinki. B. Scope

Highest ethical and scientific standards shall be endorsed for all clinical interventional investigations sponsored by MSD irrespective of the party (parties) employed for their execution (e.g., contract research organizations, collaborative research efforts). This Code is not intended to apply to trials that are observational in nature, or which are retrospective. Further, this Code does not apply to investigator-initiated trials which are not under the full control of MSD.

II. Scientific Issues

A. Trial Conduct

1. Trial Design

Except for pilot or estimation trials, clinical trial protocols will be hypothesis-driven to assess safety, efficacy and/or pharmacokinetic or pharmacodynamic indices of MSD or comparator products. Alternatively, MSD may conduct outcomes research trials, trials to assess or validate various endpoint measures, or trials to determine patient preferences, etc.

The design (i.e., participant population, duration, statistical power) must be adequate to address the specific purpose of the trial and shall respect the data protection rights of all participants, trial site staff and, where applicable, third parties. All trial protocols are and will be assessed for the need and capability to enroll underrepresented groups. Participants must meet protocol entry criteria to be enrolled in the trial. 2. Site Selection

MSD's clinical trials are conducted globally in many different countries and in diverse populations, including people of varying age, race, ethnicity, gender, and accounting for other potential disease related factors. MSD selects investigative sites based on medical expertise, access to appropriate subjects, adequacy of facilities and staff, previous performance in clinical trials, as well as budgetary considerations. Prior to trial initiation,

sites are evaluated by MSD personnel (or individuals acting on behalf of MSD) to assess the ability to successfully conduct the trial.

Where appropriate, and in accordance with regulatory authority guidance, MSD will make concerted efforts to raise awareness of clinical trial opportunities in various communities. MSD will seek to engage underrepresented groups and those disproportionately impacted by the disease under study. MSD will support clinical trial investigators to enroll underrepresented groups and expand access to those who will ultimately use the products under investigation.

3. Site Monitoring/Scientific Integrity

Investigative trial sites are monitored to assess compliance with the trial protocol and Good Clinical Practice (GCP). MSD reviews clinical data for accuracy, completeness and consistency. Data are verified versus source documentation according to standard operating procedures. Per MSD policies and procedures, if potential fraud, scientific/research misconduct, privacy incidents/breaches or Clinical Trial-related Significant Quality Issues are reported, such matters are investigated. When necessary, appropriate corrective and/or preventative actions are defined and regulatory authorities and/or ethics review committees are notified.

B. Publication and Authorship

Regardless of trial outcome, MSD commits to publish the primary and secondary results of its registered trials of marketed products in which treatment is assigned, according to the pre-specified plans for data analysis. To the extent scientifically appropriate, MSD seeks to publish the results of other analyses it conducts that are important to patients, physicians, and payers. Some early phase or pilot trials are intended to be hypothesis-generating rather than hypothesis testing; in such cases, publication of results may not be appropriate since the trial may be underpowered and the analyses complicated by statistical issues such as multiplicity.

MSD's policy on authorship is consistent with the recommendations published by the International Committee of Medical Journal Editors (ICMJE). In summary, authorship should reflect significant contribution to the design and conduct of the trial, performance or interpretation of the analysis, and/or writing of the manuscript. All named authors must be able to defend the trial results and conclusions. MSD funding of a trial will be acknowledged in publications.

III. Subject Protection

A. Regulatory Authority and Ethics Committee Review (Institutional Review Board [IRB]/Independent Ethics Committee [IEC])

All protocols and protocol amendments will be submitted by MSD for regulatory authority acceptance/authorization prior to implementation of the trial or amendment, in compliance with local and/or national regulations.

The protocol, protocol amendment(s), informed consent form, investigator's brochure, and other relevant documents must be reviewed and approved by an IRB/ERC before being implemented at each site, in compliance with local and/or national regulations. Changes to the protocol that are required urgently to eliminate an immediate hazard and to protect participants safety may be enacted in anticipation of ethics committee approval. MSD will inform regulatory authorities of such new measures to protect participant safety, in compliance with local and/or national regulations.

B. Safety

The guiding principle in decision-making in clinical trials is that participants welfare is of primary importance. Potential participants will be informed of the risks and benefits of, as well as alternatives to, trial participation. At a minimum, trial designs will take into account the local standard of care.

All participation in MSD clinical trials is voluntary. Participants enter the trial only after informed consent is obtained. Participants may withdraw from a MSD trial at any time, without any influence on their access to, or receipt of, medical care that may otherwise be available to them.

C. Confidentiality
MSD is committed to safeguarding subject confidentiality, to the greatest extent possible as well as applicable data protection rights. Unless required by law, only the investigator, sponsor (or individuals acting on behalf of MSD), ethics committee, and/or regulatory authorities will have access to confidential medical records that might identify the participant by name.

D. Genomic Research
Genomic Research will only be conducted in accordance with a protocol and informed consent authorized by an Ethics Committee.

A. Payments to Investigators

Clinical trials are time- and labor-intensive. It is MSD's policy to compensate investigators (or the sponsoring institution) in a fair manner for the work performed in support of MSD trials. MSD does not pay incentives to enroll participants in its trials. However, when enrollment is particularly challenging, additional payments may be made to compensate for the time spent in extra recruiting efforts.

MSD does not pay for participants referrals. However, MSD may compensate referring physicians for time spent on chart review and medical evaluation to identify potentially eligible participants.

B. Clinical Research Funding
Informed consent forms will disclose that the trial is sponsored by MSD, and that the investigator or sponsoring institution is being paid or provided a grant for performing the trial. However, the local ethics committee may wish to alter the wording of the disclosure statement to be consistent with financial practices at that institution. As noted above, all publications resulting from MSD trials will indicate MSD as a source of funding.

C. Funding for Travel and Other Requests
Funding of travel by investigators and support staff (e.g., to scientific meetings, investigator meetings, etc.) will be consistent with local guidelines and practices.

V. Investigator Commitment
Investigators will be expected to review MSD's Code of Conduct as an appendix to the trial protocol, and in signing the protocol, agree to support these ethical and scientific standards.

VI. Letters to Patients
At the close of the trial after unblinding, a letter is to be sent by the investigator to those participants who received placebos in the image of the competitor's product to provide the following advice:

“You have participated in a trial conducted by the Sponsor. This is to advise you that you were among those who received a look-alike [insert tablet/capsule/device/vaccine] created by the Sponsor to resemble the drug/vaccine [insert competitor drug trade name followed by its generic name in parentheses] as much as possible. You may also have received the active drug/vaccine [insert competitor drug trade name followed by its generic name in parentheses] as manufactured by [insert competitor drug manufacturer’s name].”

Appendix K: Lobe-Specific Nodal Dissection

Right-sided resection	Left-sided resection
Right Upper Lobe (RUL) Levels 2R, 3a, 4R, 7	Left Upper Lobe (LUL) Levels 3, 5, 6, 7
Right Middle Lobe (RML) Levels 2R, 3a, 4R, 7	Left Lower Lobe (LLL) Levels 7, 8, 9
Right Lower Lobe (RLL) Levels 4, 7, 8, 9	LUL & LLL (Pneumonectomy) Levels 3, 5, 6, 7, 8, 9
RUL & RML Levels 2R, 3a, 4R, 7	
RML & RLL Levels 2R, 3a, 4R, 7, 8, 9	
RUL & RML & RLL (pneumonectomy) Levels 2R, 3a, 4R, 7, 8, 9	
Important Note: Minimum acceptable nodal dissection is level 7 + another lobe specific mediastinal nodal level, which is dependent on the location of the primary lung tumor.	

Appendix L: Barrier Contraception methods

The following are considered adequate barrier methods of contraception: diaphragm, condom (by the partner), copper intrauterine device, sponge, or spermicide, as per local regulations and guidelines. Appropriate hormonal contraceptives will include any registered and marketed contraceptive agent that contains an estrogen and/or a progestational agent (including oral, subcutaneous, intrauterine, or intramuscular agents). Subjects should be informed that taking the study medication may involve unknown risks to the fetus (unborn baby) if pregnancy were to occur during the study. In order to participate in the study they must adhere to the contraception requirement (described above) for the duration of the study and during the follow-up period. If there is any question that a subject will not reliably comply with the requirements for contraception, that subject should not be entered into the study.

Appendix M: Recommendation for Contraception in United Kingdom, Portugal, Scandinavian countries and Other Applicable Countries

It is unknown whether pembrolizumab has adverse effects on a fetus in utero or on the composition of sperm. Therefore, non-pregnant, non-breast-feeding women may only be enrolled if they are willing to follow the Clinical Trial Facilitation Group (CTFG) guidance (Final Version 2014-09-15, Sections 4.1 and 4.2) for highly effective birth control as outlined below, or are considered to be highly unlikely to conceive. Highly unlikely to conceive is defined as 1) surgically sterilized, or 2) postmenopausal¹ (a woman who is ≥ 45 years of age and has not had menses for greater than 1 year will be considered postmenopausal), or 3) not heterosexually active² for the duration of the study.

(1) and (2) Refer to Portugal section below

Subjects should use birth control methods that can achieve a failure rate of less than 1% per year when used consistently and correctly and are considered as highly effective birth control methods. Such methods include:

- ◆ Combined (estrogen and progestogen containing) hormonal contraception associated with inhibition of ovulation:
 - ◆ Oral
 - ◆ Intravaginal
 - ◆ Transdermal
- ◆ Progestogen-only hormonal contraception associated with inhibition of ovulation:
 - ◆ Oral
 - ◆ Injectable
 - ◆ Implantable
- ◆ Intrauterine device (IUD)
- ◆ Intrauterine hormone-releasing system (IUS)
- ◆ Bilateral tubal occlusion
- ◆ Vasectomised partner
- ◆ Sexual abstinence³

(3) Refer to Portugal section below

Subjects should start using birth control from study Visit 1 throughout the study period up to 180 days after the last dose of study therapy.

Subjects should be informed that taking the study medication may involve unknown risks to the fetus (unborn baby) if pregnancy were to occur during the study. In order to participate in the study they must adhere to the contraception requirement (described above) for the

duration of the study and during the follow-up period defined in Section 7.2.2-Reporting of Pregnancy and Lactation to the Sponsor. If there is any question that a subject will not reliably comply with the requirements for contraception, that subject should not be entered into the study.

Monthly⁴ pregnancy testing is recommended or more frequently if required by national regulations/institution guidelines.

(4) Refer to Portugal section below

Specific guidelines for Portugal

1. For Portugal postmenopausal state is defined as no menses for 12 months without an alternative medical cause. A high follicle stimulating hormone (FSH) level in the postmenopausal range may be used to confirm a post-menopausal state in women not using hormonal contraception or hormonal replacement therapy. However in the absence of 12 months of amenorrhea, a single FSH measurement is insufficient.
2. For Portugal the absence of heterosexual activity refers to sexual abstinence.
3. For Portugal, sexual abstinence (relative to heterosexual activity) can be used as the sole method of contraception only when it is consistently employed as the subject's preferred and usual lifestyle, and if considered acceptable by local regulatory agencies and ethical committees. Periodic abstinence (e.g., calendar, ovulation, sympto-thermal, post-ovulation methods, etc.) and withdrawal are not acceptable methods of contraception.
4. For Portugal, pregnancy testing should be performed at monthly intervals.

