- ◆ Female patients with childbearing potential must have a negative urine or serum pregnancy test at screening (within 72 hours of first infusion of study medication). If the urine test cannot be confirmed as negative, a serum pregnancy test will be required. The serum pregnancy test must be negative for the subject to be eligible. Non-childbearing potential is defined as (by other than medical reasons):
 - ◆ ≥ 45 years of age and has not had menses for greater than 1 year,
 - ◆ Amenorrheic for > 2 years without a hysterectomy and oophorectomy and an FSH value in the postmenopausal range upon pretrial (screening) evaluation,
 - ◆ Whose status is post hysterectomy, oophorectomy or tubal ligation. Documented hysterectomy or oophorectomy must be confirmed with medical records of the actual procedure or confirmed by an ultrasound. Tubal ligation must be confirmed with medical records of the actual procedure otherwise the subject must be willing to use two adequate barrier methods throughout the study, starting with the screening visit through 120 days after the last infusion of study treatment. Information must be captured appropriately within the site's source documents.
- ◆ If of childbearing potential, female patients must be willing to use two adequate barrier methods throughout the study, starting with the screening visit through 120 days after the last infusion of study treatment (see [Appendix L](#)).

Note: Abstinence is acceptable if this is the usual lifestyle and preferred contraception for the subject. Please refer to [Appendix M](#) for recommendation based on Clinical Trial

Facilitation Group guidelines for sites and countries where applicable (e.g. United Kingdom, Norway, Sweden, Portugal, etc.).

- ◆ Male patients with a female partner(s) of child-bearing potential must agree to use two adequate barrier methods throughout the trial starting with the screening visit through 120 days after the last infusion of study treatment is received (see [Appendix L](#)). Males with pregnant partners must agree to use a condom; no additional method of contraception is required for the pregnant partner.

Note: Abstinence is acceptable if this is the usual lifestyle and preferred contraception for the subject. Please refer to [Appendix M](#) for recommendation based on Clinical Trial Facilitation Group guidelines for sites and countries where applicable (e.g. United Kingdom, Norway, Sweden, Portugal, etc.).

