6.7.4 Survival Follow-up

All patients who discontinued study intervention, regardless the reason of discontinuation, will move into the Survival Follow-up Phase and should be contacted by telephone every 12 weeks (+/- 2 weeks) to assess for survival status until death, withdrawal of consent, or the end of the study, whichever occurs first.

Participants should continue the follow-up visits according to the protocol. If the survival follow-up call is scheduled to occur simultaneously with a Follow-up visit, then the call can be omitted.

After year 5, survival follow-up will be conducted every 6 months by telephone.

The reference date for contacting patients for survival follow-up will follow the same schedule as the imaging schedule (Day 1 of infusion 1 (visit 1)).

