- ◆ is life-threatening (i.e. an event in which the subject was at risk of death at the time of event; it does not refer to an event which hypothetically might have caused death if it was more severe)
- ◆ requires inpatient hospitalization or prolongation of existing patient hospitalization
- ◆ results in persistent or significant disability or incapacity
- ◆ is a congenital anomaly or birth defect
- ◆ is a medically important event or reaction.
- ◆ Medical and scientific judgment should be exercised in deciding whether other situations should be considered serious such as important medical events that might not be immediately life-threatening or result in death or hospitalization but might jeopardize the patient or might require intervention to prevent one of the other outcomes listed in the definition above. Examples of such events are intensive treatment in an emergency room or at home for allergic bronchospasm, blood dyscrasias or convulsions that do not result in hospitalization, or development of drug dependency or drug abuse.

ECI: Selected serious and nonserious AEs are also known as Event of Clinical Interests (ECIs) and must be reported to the Sponsor. Events of clinical interest for this study include:

- ◆ Drug Induced Liver Injury (DILI): AST or ALT elevations ≥ 3 x ULN with concurrent elevation of total bilirubin ≥ 2 x ULN and, at the same time, alkaline phosphatase < 2 x ULN
- ◆ If grade \geq Grade 2: Nephritis, Autoimmune nephritis, Renal Failure, Acute Renal Failure, Acute interstitial pneumonitis, Interstitial lung disease, Pneumonitis
- ◆ If grade \geq Grade 2 or any grade resulting in dose modification (please refer to [Appendix H](#)) or use of systemic steroids to treat the AE: Intestinal Obstruction, Colitis, Colitis microscopic, Necrotizing colitis, Enterocolitis, Hemorrhagic enterocolitis, GI perforation, Diarrhea, Hepatitis, Autoimmune hepatitis, Transaminase elevations, Uveitis, Iritis
- ◆ If grade \geq Grade 3 or \geq Grade 2 and resulting in dose modification (please refer to [Appendix H](#)) or use of systemic steroids to treat the AE: Adrenal Insufficiency, Hyperthyroidism, Hypothyroidism, Thyroid Disorder, Thyroiditis, Hypophysitis, Hypopituitarism

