16.8 Pregnancy reporting

Pregnancy occurring during a patient's participation in this trial, although not considered an SAE, must be notified to the EORTC Pharmacovigilance Unit within the same timelines as an SAE (within 24 hours) on a Pregnancy Notification Form. The outcome of a pregnancy should be followed up carefully and any adverse outcome to the mother or the child should be reported. This also applies to pregnancies in female partners of a male patient participating in this trial.

- ◆ Any pregnancy in a female subject or in a female partner of a male subject diagnosed during the treatment period or within 120 days after last protocol treatment administration, or within 30 days after last protocol treatment administration if new anticancer therapy is initiated (whichever is earlier), must be reported to the EORTC Pharmacovigilance Unit
- ◆ This must be reported within 24 hours of first becoming aware of the event by fax, to the Pharmacovigilance Unit on a Pregnancy Notification Form
- ◆ If an SAE occurs in conjunction with the pregnancy, please also complete an SAE form as explained in the SAE reporting chapter
- ◆ Pregnancy outcomes of spontaneous abortion, missed abortion, benign hydatidiform mole, blighted ovum, fetal death, intrauterine death, miscarriage and stillbirth must be reported as serious events (Important Medical Events). If the pregnancy continues to term, the outcome (health of infant) must also be reported.

17 Quality assurance

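### Where Appendix M applies, contraception runs to 180 days after the last dose but the Section 16.8 bullet asks for pregnancy notification only to 120 days, so the duty on days 121-180 is unclear

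*Combined protocol and SAP*

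**What the plan says.** **Contraception, main text.** Section 3.3.2 requires barrier contraception "starting with the screening visit through 120 days after the last infusion of study treatment". It refers sites and countries where applicable to Appendix M.

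**Contraception, Appendix M.** Birth control is to be used "throughout the study period up to 180 days after the last dose of study therapy". Although the appendix is titled a recommendation, its text makes willingness to follow it a condition of enrolment. It defines the contraception follow-up period by reference to a Section 7.2.2, which it describes as the section on reporting pregnancy and lactation to the sponsor.

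**Pregnancy notification, Section 16.8.** The opening sentence says that a pregnancy during a patient's "participation in this trial, although not considered an SAE, must be notified to the EORTC Pharmacovigilance Unit" within 24 hours, and gives no day limit. The first bullet is narrower. It covers pregnancies in a female patient, or in the partner of a male patient, "diagnosed during the treatment period or within 120 days after last protocol treatment administration". That limit drops to 30 days if new anticancer therapy is started, whichever comes first.

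**Outcomes, Section 16.8.** "The outcome of a pregnancy should be followed up carefully and any adverse outcome to the mother or the child should be reported". The last bullet lists miscarriage, fetal death, stillbirth and similar outcomes as serious events. It also requires the infant's health to be reported if the pregnancy goes to term.

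**The concern.** Under the main-text rule, the period in which a patient must avoid pregnancy and the period in which a pregnancy must be notified end on the same day. Appendix M lengthens the first period and nothing lengthens the second. A site in an Appendix M country therefore has patients who must still use contraception, while the bullet no longer asks for notification if contraception fails.

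The broken cross-reference makes this harder to resolve. A coordinator who follows Appendix M to Section 7.2.2 finds the general evaluation of adverse events and no pregnancy window.

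At stake is the 24-hour notification of a pregnancy with no complication at diagnosis, and the outcome follow-up that starts from it. Appendix M itself says the effect of pembrolizumab on a fetus is unknown. Section 6.3 ties monthly pregnancy testing to protocol treatment, and the follow-up schedule in Table 5 lists no pregnancy test. Appendix M recommends monthly testing but gives no end date. After treatment, capture therefore depends largely on sites knowing what they must notify.

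**Working it through.** The check is a comparison of stated windows. No power, alpha or sample-size figure is involved.

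**Inputs, in days after the last study treatment**

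| Item | Source | Limit |
|---|---|---|
| Contraception, main text | Section 3.3.2 | 120 |
| Contraception, Appendix M | Appendix M | 180 |
| Notification, all sites | Section 16.8, first bullet | 120 |
| Notification after new anticancer therapy, all sites | Section 16.8, first bullet | 30 |
| Notification, opening sentence | Section 16.8 | none stated |

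**Gap = contraception limit - notification limit**

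- Main text, no new therapy: 120 - 120 = 0 days.
- Appendix M, no new therapy: 180 - 120 = 60 days, that is, days 121-180.
- Share of the Appendix M post-treatment contraception period: 60 / 180 = 33%.

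**New anticancer therapy, shown separately**

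- Main text: up to 120 - 30 = 90 days.
- Appendix M: up to 180 - 30 = 150 days.
- Difference: 150 - 90 = 60 days.

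The 30-day limit applies at every site. Appendix M adds 60 days in either case, so 60 days is the part specific to Appendix M.

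**Does the opening sentence of 16.8 settle days 121-180?** Section 6.7.4 keeps patients who stop treatment in survival follow-up "until death, withdrawal of consent, or the end of the study, whichever occurs first". Participation therefore normally extends past day 180, and the opening sentence can be read to cover those days. On that reading, however, the bullet's 120-day and 30-day limits would have almost nothing to do for patients still in follow-up. The text supports two readings and does not choose between them.

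**Are adverse outcomes lost?** No. The outcome sentence and last bullet of 16.8 carry no day limit and no relatedness test. Section 16.1 also lists an event that "is a congenital anomaly or birth defect" as a serious adverse event. That definition alone would not guarantee reporting, because from day 91 Section 16.6 limits reporting to events with a reasonable possibility of relation to treatment or study participation. Coverage rests on 16.8.

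**After the fix:** 180 - 180 = 0 days where Appendix M applies and no new therapy has started.

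**The case against.** The strongest reply is that the broad duty is already written. The opening sentence of 16.8 covers any pregnancy during participation and survival follow-up continues well past day 180, so the real conflict is inside 16.8 and exists at every site. This stands in part, and it is why the duty is called unclear and not missing. At main-text sites, though, the bullet at least covers the whole contraception period for patients without new therapy. At Appendix M sites it does not.

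The bullet might also be a minimum window for patients who have withdrawn consent and so left the trial, which would give its limit a purpose. The protocol does not say so, and the reading is strained, because the bullet shortens its own window to 30 days after new therapy.

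A third reply is that contraception and notification periods serve different purposes and no stated rule makes them equal; the 30-day limit shows that they already differ in some cases. It is true that no rule is stated. But the two limits coincide at 120 days in the main text, and Appendix M tries to define its contraception follow-up by the pregnancy-reporting section, which suggests they were meant to correspond.

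Finally, the consequence is small. That is correct. Infant health at term and adverse outcomes are reportable without a stated window, so what may be lost is timely notice of an uncomplicated pregnancy at sites that follow the bullet.

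**Conclusion.** The concern holds. Where Appendix M applies, the last 60 days of required contraception (days 121-180) lie outside the notification window in the 16.8 bullet, against 0 days under the main-text rule. Both figures are for patients who have not started new anticancer therapy. The open-ended sentence at the head of 16.8 leaves the duty unclear, and the misdirected reference in Appendix M does not resolve it.

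The 60 days, or 33% of the post-treatment contraception period, is calendar time and not risk. The documents give neither the number of patients of childbearing potential nor the number in Appendix M countries, so no count of affected pregnancies can be estimated. No endpoint, analysis or error rate is touched. This is a minor safety-reporting inconsistency that is worth correcting because the correction is so small.

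**What to change.** Make two edits in the same amendment:

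1. In Section 16.8, add one sentence: where Appendix M applies, pregnancies are reportable through 180 days, instead of 120, after the last protocol treatment administration.
2. In Appendix M, change the reference from Section 7.2.2 to Section 16.8.

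The edits belong together, because correcting the reference alone would set a 180-day contraception period directly beside a 120-day reporting limit. The 120-day limit at other sites and the general 30-day limit after new anticancer therapy can stay as they are; the mismatch that the 30-day limit creates is a separate matter and these edits do not remove it.

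The cost is one sentence and one cross-reference. Any extra notifications would come only from Appendix M countries; their number cannot be estimated from the documents.
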